#### ***15.5.4.3 Unblinding for Final Analysis***

Treatment unblinding and release of the randomization codes of the investigational product assignments for the study will occur if the trial is terminated or, at the time of database lock. That is after all randomized subjects have completed the study or discontinued from the study and all clinical data have been received and data inconsistencies have been resolved.

## **15.6 Interim Analysis**

An interim analysis will be conducted when approximately 50% of subjects have been randomized and completed Visit 13 (Week 24) or early terminated, whichever comes first.

The procedures for this interim analysis will be based on a standard operating procedure that has a well-established firewall to protect the integrity of the trial. The interim analysis will be performed by an independent statistician, who is not otherwise associated with the conduct of this trial.

The main purpose of this interim analysis is to assess:

- sample size re-assessment to evaluate the sample size estimations, which will serve in the planning of the remainder of the study
- other parameters that the Data Monitoring Committee may request

### **15.6.1 Procedures for Interim Analysis**

- Cutoff dates for collection of electronic CRFs, data querying, database lock, and analysis are established based on an estimated target date of the approximately 50% of subject completing 24 weeks of treatment or early terminated.
- All data available by the cutoff date is entered, validated, queries generated and resolved or pending queries documented.
- The database is locked.
- The locked database is saved in a drive to which only the independent statistician responsible for the interim analysis has access.

Using the data obtained in this interim analysis, the independent statistician will prepare safety summaries and calculate the following metrics for the primary endpoint:

- Mean percent change at Week 24, the SD and the observed number of subjects in the active arm.
- Mean percent change at Week 24, the SD and the observed number of subjects in the placebo arm.
- The dropout rate at the time of the interim analysis for both arms.
- The conditional power (CP) analysis of the study at the time of the interim analysis (17) (the method for this calculation is provided in below).
- The revised sample size requirement based on this interim analysis (18) (the rule and method for sample size recalculation are provided below).

### **15.6.2 Conditional Power Calculation**

The CP will be calculated according to the below formula using the mean percent changes in the active arm compared to placebo arm:

$$CP(f_I, z_I) = \Phi \{ z_I / \sqrt{f_I (1 - f_I)} - z_\alpha / \sqrt{(1 - f_I)} \}$$

where:

- $CP(f_I, z_I)$  is the CP at the interim analysis
- $\Phi \{ \cdot \}$  is the cumulative distribution function of a standard normal distribution ( $\mu = 0, \sigma^2 = 1$ )
- $f_I$  is the fraction of subjects enrolled and used in the interim analysis before decision of increasing the sample size
- $z_\alpha$  is the upper  $\alpha$  quintile for standard normal distribution
- $z_I$  is the standardized normal, the z score will be obtained from the following formula:

$$z_I = (\mu_a - \mu_c - 3) / \sqrt{[\sigma_a^2 / n_a + \sigma_c^2 / n_c]}$$

where:

- $\mu_a$  = the mean percent changes at Week 24 for the subjects in the active arm

---

- $\mu_c$  = the mean percent changes at Week 24 for the subjects in the placebo arm
- $\sigma_a$  = the SD of percent changes at Week 24 for the subjects in the active arm
- $\sigma_c$  = the SD of percent changes at Week 24 for the subjects in the placebo arm
- $n_a$  = the number of subjects in the active arm used in the interim analysis
- $n_c$  = the number of subjects in the placebo arm used in the interim analysis
- $a$  = the active arm
- $c$  = the placebo arm

The resulting CP will be used to determine whether the sample size should be increased or remain unchanged.

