### 5.2.1.2 Effect on Body Weight

This study (FLOW = First Loss Of Weight) was aimed to assess the effect of repeated administration of Gelesis100 on body weight (10). The study was conducted at 5 sites in 3 European countries (Denmark, Czech Republic, and Italy). One hundred twenty-eight subjects were randomized into 3 arms: Gelesis100 2.25 g, Gelesis100 3.75 g, or placebo. Subjects received 5 capsules of Gelesis100 or placebo before lunch and dinner, in a double-blind and parallel-group fashion. A hypocaloric diet (-600 kcal/day) was prescribed to all subjects. The duration of the treatment was 12 weeks. One hundred twenty five subjects had at least one post-baseline assessment of body weight (intention-to-treat “ITT” population). Forty-two of the ITT subjects were on Gelesis100 2.25 g, 41 on Gelesis100 3.75 g, and 42 on placebo (Table 6). One hundred ten subjects completed the key visit of the study at Day 87 for the assessment of body weight. One hundred twenty-six subjects provided safety data. The primary efficacy endpoint was assessed by analysis of covariance (ANCOVA) model in the ITT population with baseline weight, gender, and BMI status as covariates.

**Table 6.** General characteristics of the ITT population at baseline.

Parameter	Gelesis100 2.25 g (n = 42)	Gelesis100 3.75 g (n = 41)	Placebo (n = 42)
Male (n)	13 (31%)	14 (34%)	13 (31%)
Female (n)	29 (69%)	27 (66%)	29 (69%)
Age (years)*	42.4 ± 12.3	46.1 ± 11.2	44.0 ± 11.7
BMI*	31.2 ± 2.3	31.8 ± 2.5	32.0 ± 2.3
Overweight (n)	14 (33%)	12 (29%)	12 (29%)
Obese (n)	28 (67%)	29 (71%)	30 (71%)
Glucose (mg/dL)*	93 ± 10	94 ± 9	96 ± 10
Glucose (mmol/L)*	5.18 ± 0.54	5.20 ± 0.50	5.31 ± 0.58

\*Mean ± SD.

Body weight decreased significantly at Day 87 in subjects on Gelesis100 2.25 g with a placebo-adjusted weight loss of 2.0% and a total body weight loss of 6.1% (Table 7).

**Table 7.** Body weight (% change from baseline) at Day 87 in the ITT population.

Arm	Number of subjects	Mean $\pm$ SD	P value (versus placebo)
Gelesis100 2.25 g	42	-6.1 $\pm$ 5.1	0.026
Gelesis100 3.75 g	41	-4.5 $\pm$ 4.5	0.859
Placebo	42	-4.1 $\pm$ 4.4	-

Subjects on Gelesis100 2.25 g had higher rate of weight loss  $\geq 10\%$  and lower rate of weight gain (Table 8). Lower tolerability and compliance may explain the observed efficacy result with Gelesis100 3.75 g.

**Table 8.** Body weight response at Day 87 in the ITT population.

Parameter	Gelesis100 2.25 g (n = 42)	Gelesis100 3.75 g (n = 41)	Placebo (n = 42)

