## **15.4 Sample Size Determination and Rationale**

For this clinical trial, a total of 460 subjects (230 per arm) will be randomized to have 322 subjects complete the study (161 per arm) due to an anticipated dropout rate of 30%. This sample size will allow establishing both super-superiority and superiority with sufficient statistical power based on the primary endpoint of change in body weight from baseline.

The sample size calculation, using PASS (16), is based on the assumption that there will be a clinically meaningful difference of at least 3.0% weight loss between the two arms after 24 weeks of treatment. This 3.0% is also being used as margin to establish the super-superiority (lower bound of the confidence interval of Gelesis100 effect  $\geq 3.0\%$  of placebo effect). With the above sample size, there is 85% statistical power for a 3.0% margin super-superiority (i.e., delta of at least 4.5%) with a common SD of 5.0% and a type I error rate of 0.05 (one-sided test). The statistical formula for the study hypothesis is as follows:

$$H_0: \mu_{\text{placebo}} - \mu_{\text{Gelesis100}} < 3.0\%$$

$$H_A: \mu_{\text{placebo}} - \mu_{\text{Gelesis100}} \geq 3.0\%$$

Where  $\mu_{\text{placebo}}$  is the mean percent change from baseline in the placebo arm and  $\mu_{\text{Gelesis100}}$  is the mean percent change from baseline in the Gelesis100 arm.

In addition, with the above sample size, there will be at least 90% statistical power to establish that the difference between the two arms is greater than 0 (i.e., the superiority with no margin), with a common SD of 5.0% and a type I error rate of 0.05 (two-sided tests), with the null hypothesis that the mean percent change from baseline in primary effectiveness endpoint is the same for both treatment arms and the alternative hypothesis that the Gelesis100 arm provides a different mean percent change in body weight than does the placebo arm. The statistical formula for the study hypothesis is as follows:

$$H_0: \mu_{\text{placebo}} - \mu_{\text{Gelesis100}} = 0$$

$$H_A: \mu_{\text{placebo}} - \mu_{\text{Gelesis100}} \neq 0$$

Where  $\mu_{\text{placebo}}$  is the mean percent change from baseline in the placebo arm and  $\mu_{\text{Gelesis100}}$  is the mean percent change from baseline in the Gelesis100 arm.

---

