#### **15.6.3 Rule and Method for Increasing Sample Size**

- If the CP  $< 36\%$ , the sample size will not be increased and the study will continue as is.
- If the CP is  $\geq 36\%$  and  $< 85\%$ , the sample size may be adjusted to retain the original power of 85%.
- If the CP is  $\geq 85\%$ , the study will continue as is.

Regardless of the size of the CP, the study sample size will not be reduced.

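### The interim conditional-power z-score subtracts the arms in the opposite order from the trial hypothesis, so conditional power is about 0 for any benefit and the sample-size rule cannot fire for a working product

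*Combined protocol and SAP*

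**What the plan says.** Section 15.4 sets the super-superiority hypothesis as placebo minus Gelesis100 of at least 3.0%. The placebo term "is the mean percent change from baseline in the placebo arm", and the Gelesis100 term is defined in the same way. A benefit makes this difference positive only if weight loss is a negative change. The earlier FLOW study is reported on that scale: Table 7 in section 5.2.1.2, "Body weight (% change from baseline) at Day 87 in the ITT population", shows -6.1 for Gelesis100 2.25 g and -4.1 for placebo.

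Section 15.6.2 calculates CP "using the mean percent changes in the active arm compared to placebo arm". Its z-score is (mu_a - mu_c - 3) divided by the standard error. Here mu_a is "the mean percent changes at Week 24 for the subjects in the active arm", and mu_c is the corresponding placebo mean. Section 15.6.1 likewise asks the independent statistician for the mean percent change in each arm. Nothing in the protocol recodes these inputs as positive percent loss.

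Section 15.6.3 then acts on CP alone:
- Below 36%, "the sample size will not be increased and the study will continue as is".
- From 36% to below 85%, the size may be raised to restore 85% power.
- At 85% or more, the study continues unchanged.

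**The concern.** The two sections use the same quantity and the same margin but subtract the arms in opposite orders. Under any single sign convention they cannot both be right. If change is negative for loss, as sections 15.4 and 5.2.1.2 have it, the interim numerator at the planned effect is -4.5 - 3 = -7.5, where it should be 4.5 - 3 = +1.5.

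This matters because CP is the only trigger for the sample-size decision, and section 15.6 names sample-size re-assessment as a main purpose of the interim analysis. Section 15.6.7 also justifies the absence of a type I error adjustment partly on the ground that the increase happens when CP is promising. Followed literally, the rule returns a CP near 0 for every beneficial result and calls a result promising only when the product is clearly worse than placebo.

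**Working it through.** **Inputs.** From section 15.4: "a total of 460 subjects (230 per arm) will be randomized", with 30% dropout leaving 161 completers per arm; "there is 85% statistical power for a 3.0% margin super-superiority (i.e., delta of at least 4.5" percent), "with a common SD of 5.0% and a type I error rate of 0.05 (one-sided test"). From section 15.6: an interim at about 50%. I take f = 0.5 and 161/2 = 80.5 completers per arm. Section 15.6.2 does not state the alpha behind z_alpha, so I use the one-sided 0.05 of section 15.4, giving z_alpha = 1.645.

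**The plan's own power figure.** The standard error at the end is 5 × √(2/161) = 0.557. The effect above the margin is 4.5 - 3.0 = 1.5. Power = Φ(1.5/0.557 - 1.645) = Φ(1.047) = 85.2%, so the stated 85% reproduces.

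**CP at the planned effect.** The interim standard error is 5 × √(2/80.5) = 0.788. The plan's formula is CP = Φ{z/√(f(1-f)) - z_alpha/√(1-f)}, which at f = 0.5 is Φ(2z - 2.326).

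| Order of subtraction | Numerator | z | CP |
|---|---|---|---|
| As written in 15.6.2 (active - placebo - 3) | -4.5 - 3 = -7.5 | -9.52 | Φ(-21.4), effectively 0 |
| As in 15.4 (placebo - active - 3) | 4.5 - 3 = +1.5 | 1.90 | Φ(1.48) = 93.1% |

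**CP over a range of observed benefits** (placebo minus active, in points).

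| Observed benefit | CP as written | CP in the order of 15.4 |
|---|---|---|
| 3.0 | 0 | 1.0% |
| 3.5 | 0 | 14.5% |
| 3.8 | 0 | 38.4% |
| 4.0 | 0 | 58.4% |
| 4.2 | 0 | 76.4% |
| 4.5 | 0 | 93.1% |
| 6.0 | 0 | 100% |

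**Where the increase zone lies.** Solving CP = 36% and CP = 85% for z gives 0.984 and 1.681. These correspond to differences of 3 + 0.984 × 0.788 = 3.78 and 3 + 1.681 × 0.788 = 4.32 points. In the order of section 15.4, that is a benefit of about 3.8 to 4.3 points. As written, it is a deficit of the same size.

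**How often the zone is reached with the consistent sign.** At a true 4.5, z is normal with mean 1.903 and SD 1, so the probability is Φ(1.681 - 1.903) - Φ(0.984 - 1.903) = 0.412 - 0.179 = 23%. At a true 4.0 the mean is 1/0.788 = 1.269, and the probability is 0.660 - 0.388 = 27%.

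**Power forgone.** The plan gives no maximum size, so a cap has to be assumed. The simulated rule raises the size until CP at the observed trend reaches 85%, or to the cap.

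| True effect | No increase | Cap 1.5 × plan | Cap 2 × plan |
|---|---|---|---|
| 4.5 | 85% | 88% | 88% |
| 4.0 | 56% | 60% | 61% |

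**Sensitivity at the planned effect.** With f from 0.4 to 0.6, CP in the order of section 15.4 runs from 91% to 95%. With 115 per arm (no dropout) it is 98.7%. With one-sided alpha 0.025 it is 85.0%. As written it is 0 in every case.

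**The case against.** The strongest reply is that the contrast at the planned effect changes no decision. A CP of 0 and a CP of 93% both lead to continuing unchanged under section 15.6.3. That is correct: the action differs only when the observed benefit is about 3.8 to 4.3 points.

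The loss is also bounded. The increase is optional, there is no stopping for effectiveness, low CP does not stop the trial, and the sample size is never reduced. If the rule never fires, power at the design effect stays at the planned 85%. The final ANCOVA does not use the interim z-score, and for a beneficial product the error only withholds an increase, so it does not inflate type I error. All of this stands, and it limits the consequence to the interim sample-size decision.

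It can also be said that the objectives speak of placebo-adjusted weight loss as a positive number, that the written formula works if loss is entered as positive, and that a z near -9.5 beside a visible benefit would be noticed. This lowers the practical risk but does not remove the contradiction. Both sections define their inputs as percent change. A prespecified adaptive rule should not depend on an undocumented correction made after unblinding by the one statistician who has seen results by arm.

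**Conclusion.** The concern holds. Section 15.6.2 reverses the direction of the hypothesis in section 15.4, and no other text reconciles them. As written, CP is effectively 0 for any benefit, and the increase zone is reached only if placebo beats Gelesis100 by about 3.8 to 4.3 points. The interim's only prespecified sample-size trigger is therefore disabled for a working product.

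The cost is about 3 points of power at a true 4.5 and about 5 points at a true 4.0. Those figures rest on f = 0.5, 80.5 completers per arm, SD 5.0, one-sided alpha 0.05, an increase taken whenever the rule allows it, and an assumed cap of twice the plan. A cap of 1.5 times gives much the same answer. The finding that CP is about 0 as written does not depend on the alpha, information fraction or dropout within the ranges checked.

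**What to change.** In section 15.6.2, write the z-score as (mu_c - mu_a - 3) over the same standard error, that is placebo minus active as in section 15.4, and state that percent change is negative for weight loss. Keeping the formula and redefining mu_a and mu_c as mean percent weight loss would work equally well; section 15.6.1 should then use the same definition. State in the same place the alpha behind z_alpha, because corrected CP at the planned effect is 93% with one-sided 0.05 and 85% with one-sided 0.025.

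The correction must be made before the interim analysis is run. It is a change of one line, with no extra patients and no operational consequence.

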#### **15.6.3 Rule and Method for Increasing Sample Size**

- If the CP  $< 36\%$ , the sample size will not be increased and the study will continue as is.
- If the CP is  $\geq 36\%$  and  $< 85\%$ , the sample size may be adjusted to retain the original power of 85%.
- If the CP is  $\geq 85\%$ , the study will continue as is.

Regardless of the size of the CP, the study sample size will not be reduced.

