#### **Co-primary endpoints**

ANCOVA will be used to compare the percent change in weight from baseline to Day 171 for the two treatment arms. The stratification factors and baseline weight will be included in the analysis and associated treatment difference, 95% confidence interval around the difference and *P* value for the treatment effect will be reported.

The proportion of body weight responders will be presented descriptively by treatment arm. Responders in this case will be defined as those subjects who have achieved  $\geq 5\%$  reduction in body weight compared to baseline. In addition, the Logit model will be used to analyze the percent of responders, with the stratification factors and baseline weight in the model.

To maintain the trial-wise type I error rate at 0.05, a closed test procedure will be used for the secondary and tertiary endpoints. The order of the endpoints will be as follows:

---

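### The interim rule for raising the sample size states no maximum and no recalculation formula, and its z score is not the primary ANCOVA statistic in either form or sign

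*Combined protocol and SAP*

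**What the plan says.** Section 15.4 states that "a total of 460 subjects (230 per arm) will be randomized". It also says that "there is 85% statistical power for a 3.0% margin super-superiority (i.e., delta of at least 4.5" percent, "with a common SD of 5.0% and a type I error rate of 0.05 (one-sided test". The effect there is the placebo mean minus the Gelesis100 mean of percent change from baseline.

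Section 15.6 plans one unblinded interim analysis at about 50% of subjects. Among the metrics listed in 15.6.1 are "Mean percent change at Week 24, the SD and the observed number of subjects in the active arm", the same for placebo, the CP and a revised sample size. Of the last, 15.6.1 says that "the rule and method for sample size recalculation are provided below".

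Section 15.6.2 gives the CP formula. Its z score is the active mean minus the placebo mean minus 3, divided by the unadjusted two-sample standard error. No value is given for alpha.

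Section 15.6.3 then sets three zones. Below 36% and from 85% upwards the study continues unchanged; between them, "the sample size may be adjusted to retain the original power of 85" percent. The only bound on N is that it will not be reduced.

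For the final analysis (15.8.6.1, Co-primary endpoints), "ANCOVA will be used to compare the percent change in weight from baseline to Day 171 for the two treatment arms", with the stratification factors and baseline weight in the model.

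**The concern.** A rule that aims at a fixed CP across the whole middle zone asks for most subjects where the interim result is weakest. Without a maximum, the increase implied near the lower limit may be one that no sponsor could carry out. Without a formula, the size of the increase is left to judgement once unblinded results exist. Pre-specification is meant to remove that judgement.

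The CP should also project the statistic that will be tested. Here it projects a raw mean comparison, while the final test is covariate-adjusted. The two can place the same interim data in different zones. The sign of the printed z score also needs checking, because a reversed sign would put an effective product in the lowest zone.

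**Working it through.** **Inputs.** One-sided alpha 0.05 (z = 1.645), margin 3.0, assumed effect 4.5, SD 5.0, 460 randomized and 161 completers per arm (all 15.4); interim fraction f = 0.5 (15.6); CP formula (15.6.2); zone limits (15.6.3). Half of 161 gives 80.5 evaluable per arm at the interim.

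**The plan's own figure.** Power = Φ(1.5 / (5·√(2/161)) − 1.645) = 85.2%. The stated 85% reproduces, and it is the one-sided 0.05 figure; one-sided 0.025 gives 76.8%.

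**N needed at the lower limit.** The formula is CP = Φ{z/√(f(1−f)) − z_α/√(1−f)}.
- Setting CP = 0.36 at f = 0.5: 2z − 2.326 = −0.358, so z = 0.984.
- Hold z and the 230 interim subjects fixed, and solve for f = 230/N at CP = 0.85. At N = 1,612, f = 0.1427 and Φ(0.984/0.350 − 1.645/0.926) = Φ(1.037) = 0.85.

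| CP at interim | N, one-sided 0.05 | N, one-sided 0.025 |
|---|---|---|
| 36% | 1,612 (3.50×) | 1,331 (2.89×) |
| 50% | 1,122 (2.44×) | 984 (2.14×) |
| 60% | 890 (1.94×) | 809 (1.76×) |
| 70% | 705 (1.53×) | 663 (1.44×) |

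At one-sided 0.05, CP 36% gives 1,694 if f = 0.4 and 1,526 if f = 0.6. Section 10.2 plans about 1.5 years to enrol 460. At that rate 1,612 takes 1,612 × 1.5/460 = 5.3 years, and 1,331 takes 4.3 years.

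**How often more than double is needed.** At one-sided 0.05, a factor of 2 is needed at z = 1.271 (CP 58.6%). At a true effect of 4.5 the interim z has mean 1.5/(5·√(2/80.5)) = 1.903. The chance of falling between 0.984 and 1.271 is Φ(−0.632) − Φ(−0.919) = 8.5%. At a true effect of 4.0 it is 11%.

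**What a 2-fold cap changes** (simulation, one-sided 0.05):
- Effect 4.5: power 88.5% uncapped, 88.4% capped; mean N 1.20 and 1.15 times plan.
- Effect 4.0: power 62.2% and 61.3%; mean N 1.26 and 1.18 times plan.
- True difference equal to the margin: rejection about 0.048 either way.

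**Lower CP limit that suits a 2-fold cap.** An increase does not raise the conditional type I error if (z_α − √f*·z)/√(1−f*) ≥ (z_α − √f·z)/√(1−f), with f = 0.5 and f* = 0.25.
- One-sided 0.05: 1.900 − 0.577z ≥ 2.326 − z, so z ≥ 1.010, which is CP 38%.
- One-sided 0.025: z ≥ 1.203, which is CP 36%.
- With no cap, the limits are about 31% and 29%.

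**Raw against adjusted z.** The documents give no R², so 5%, 10% and 20% are assumed; the two z scores then correlate at √(1−R²). At a true effect of 4.5 they fall in different zones in 12%, 17% and 24% of interims. With the final test always the ANCOVA, power with raw and adjusted interim z is 89.7% and 89.8% (R² 5%), 90.9% and 91.1% (10%), and 93.2% and 93.5% (20%). The largest loss at effects of 3.75 to 4.5 is about 0.6 points, and mean N differs by at most 0.03 times plan.

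**Sign.** In 15.4 the benefit is placebo minus active, so weight loss is a negative change. Under that convention a true benefit of 4.5 points gives, in the printed formula, z = (−4.5 − 3)/0.788 = −9.5 and a CP of practically zero. With the sign of 15.4, z = 1.5/0.788 = 1.90 and CP is 93%.

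**The case against.** The rule is permissive, and under 15.6.6 the Data Monitoring Committee only makes recommendations. A reader might infer that the protocol commits to about 1,600 subjects. It does not; that is what restoring 85% would take at the edge of the zone, on one reading.

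Another reading is open. The original 85% was set at an effect of 4.5. At the same interim z of 0.984, restoring 85% under that effect needs only 1.27 times the plan, about 583 subjects. This objection stands against any single headline N, but it shows why the missing formula matters: the text is compatible with 583 and with 1,612.

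A reader might also infer that the open-ended increase inflates type I error, or that the sponsor would choose N knowing the results. Neither is supported. The 36% limit lies above the threshold for an uncapped increase. Section 15.5.3 keeps the sponsor blinded, 15.5.4.1 gives unblinded assignments for this analysis only to the independent statistician, and 15.6 describes a firewall. The committee may, however, ask to see unblinded arms.

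The zone disagreement sounds worse than it is. A reader might take a rate of 12 to 24% as serious harm, but the power figures do not bear that out, and R² is assumed.

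Finally, the protocol refers to a separate SAP (section 15) and a committee charter (15.6.4, 16.2), neither of which is in the text reviewed. A maximum could be stated there. Against that, 15.6.1 says the method is given in the protocol, and 15.6.4 assigns to the charter the content of the committee's report.

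**Conclusion.** The point holds as a gap in feasibility and pre-specification. Section 15.6.3 targets 85% across CP 36% to 85% with neither a maximum N nor a recalculation formula. On the observed-effect reading at f = 0.5, the lower limit implies about 1,610 subjects at one-sided 0.05 or 1,330 at 0.025. At one-sided 0.05 and a true effect of 4.5, more than double the plan is needed in about 8% of trials. Type I error is not the problem: it stays near 0.048 if the rule is followed.

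The raw-mean z score is a lesser fault. Correcting it needs no new data and gains at most about 0.6 points of power under the assumed R².

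The sign in 15.6.2 contradicts 15.4 if weight loss is recorded as a negative change. A reader might conclude that no increase could ever be triggered. That follows only if the formula is programmed literally under that convention, so the two sections need to be reconciled.

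**What to change.** Make these changes before the interim data are unblinded.

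1. In 15.6.1 and 15.6.2, compute z_I as (ANCOVA-adjusted placebo minus Gelesis100 difference − 3)/SE, both taken from the primary model fitted to the locked interim data. This also aligns the sign with 15.4. State the alpha behind z_α.
2. In 15.6.3, give the recalculation formula, including the effect under which 85% is to be restored.
3. In 15.6.3, state a maximum, for example 920 randomized subjects (2 × 460); another stated multiple would also serve. Match the lower CP limit to that maximum and alpha: with a 2-fold cap, about 38% at one-sided 0.05, or 36% at one-sided 0.025. Adding the cap while keeping 36% at one-sided 0.05 would leave CP 36% to 38% outside the region where the argument in 15.6.7 holds analytically, although the simulated overall error stays near 0.048.

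The cost is wording in the protocol, and in the SAP and charter where they repeat the rule. A 2-fold cap gives up about 0.1 points of power at an effect of 4.5 and 0.9 at 4.0.
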